#### 4.2.12 Biomarker Research

## 4.3 Biological sampling procedures

#### 4.3.1 Immunogenicity sampling and evaluation methods

Those enrolled on the Phase I (where Tissue allows) or the Phase II randomized study will be required to undergo a core biopsy of a target or nontarget lesion prior to starting treatment and between cycle 1 days 15-21.

The pretreatment biopsy or archival sample needs to have occurred after the most recent line of therapy, and be either an FFPE sample or slide cut within 6 months of the assay for PD-L1

Pharmacodynamic endpoints will then be assessed in the tumor tissue. We will determine whether tumor immunogenicity prior to treatment is associated with the response to pembrolizumab ± vorinostat, and whether vorinostat treatment leads to *greater* enhancement in immunogenicity after treatment. We broadly define tumor immunogenicity to include both T cell presence and the expression of immune response-promoting genes. To this end, we will perform tumor biopsies prior to treatment and again at C1 Day15-21 after initiation of treatment (i.e. on-treatment). NanoString assay will be used to determine expression of potentially important immune function genes, including a recently defined NF-kB gene expression signature in lung cancer cells that is associated with greater T cell presence in human lung adenocarcinoma. An additional key goal is to determine association of pre- or on-treatment expression of other immune checkpoints genes (e.g. BTLA, LAG3, TIM3) with resistance to pembrolizumab ± vorinostat treatment. These important studies can provide a framework to assess how pembrolizumab ± vorinostat modulate the tumor microenvironment, characterize potential utility of biomarkers in response to treatment (e.g. NF-kB activity), and identify resistance mechanisms.

# 4.3.2 Biomarker/Pharmacodynamic sampling and evaluation methods

**Molecular studies.** The following molecular test results including but not limited to ALK, EGFR, K-ras, ROS-1, PD-L1 status, RET, Met, PTEN, BRAF, PI3K and Her2 neu will be conducted when appropriate or collected when available in the medical record. PD-L1 status by immunohistochemistry and quantitation of tumor infiltrating lymphocytes will be determined on all biopsy specimens.

PD-L1 expression will be measured in all fresh and archival biopsies using the IHC assay based on the anti-PD-L1 monoclonal antibody (most likely the Merck anti-PD-L1 clone 22C3). Positive staining with this assay is currently defined as tumor cell membrane staining at any intensity, analyzed with a cut-off value of ≥ 1% in a minimum number of 100 evaluable cells. Baseline tumor PD-L1 expression will be evaluated for potential association with ORR, PFS, and overall survival (OS).

Further, exploratory correlative studies may be completed based on the additional data obtained including utilization of an advanced DNA platform or additional immune based biomarker analyses. These results would also be correlated with patient outcomes and potentially help to address some of the critical barriers for effective personalized treatment.

Histone acetylation studies on PBMC's. Previous studies have indicated that HDAC inhibitors lead to the acetylation of many molecules including of histone 3 and 4. Biomarker assessments will be made on blood for assessment of pre and post-treatment effects on acetylated histone 3 (H3) and histone 4 (H4), total H3 and H4. Correlative analysis will be performed on the peripheral blood mononuclear cells (PBMC) of all the patients enrolled in the study. This will include flow cytometry based assessment of presence of suppressive cell types such as myeloid-derived suppressor cells (MDSC) and Tregs. In addition, we will determine expression of activation and resistance markers in lymphocytic lineages, including T cells, by flow cytometry and gene expression studies. Plasma will also be collected to determine levels of key cytokines and chemokines. The blood draws will take place pretreatment (either during screening or on C1D1) and during treatment (C1D15+/- 7 days). Peripheral blood mononuclear cells will be isolated from patient blood collected prior to and after initiation of therapy to measure H3 and H4 histone acetylation by western blot analysis by [name] lab as previously described Gray et al, CCR, 2014(Gray et al., 2014).

# 4.3.3 Eco-evolutionary modeling methods

Toward secondary objective #3, the following steps will be taken:

The initial step will use available clinical and correlative data to examine (in the context of estimated immune response to therapy) the changes in frequency of subpopulations within each lung cancer on biopsies taken prior to therapy, during therapy, and (where available) at the time of tumor progression. This will be used to parameterize models using (non-spatial) Ordinary Differential Equations of the evolutionary dynamics.

In the second step, we will apply image analytic methods to the existing pathology slides. This will allow development of spatially-explicit mathematical models including Partial

Differential Equation and Agent-based methods to capture the ecological as well as evolutionary dynamics.

A final step involves testing model predictions or exploring hypotheses developed through model simulations by performing additional studies on available samples, for example, obtaining new IHC stains on the pathology slides.

# 4.3.4 Archival Tumor Samples and Fresh Tumor Biopsies

# 4.3.4.1 Archival tumor samples and Fresh tumor biopsies

Archived tissue will be collected from all patients enrolled on the study. For those enrolled on the phase I escalation portion without available archival tissue, fresh tumor specimens will be collected by image-guided biopsy with onsite pathologic confirmation by a trained cytotech or board certified cytopathologist. Approximately 125 µL of tumor sample is required at baseline for PDL1 testing and to evaluate potentially predictive biomarkers and complete other correlative studies. In addition, patients enrolled on the phase I dose escalation, Phase Ib expansion and randomized phase II portions of the trial will undergo serial biopsies. More specifically, those enrolled on the phase I dose escalation, Phase Ib expansion and Phase II randomized study will be required to undergo a core biopsy of an accessible lesion prior to starting treatment (or collection of archival tissue from after the most recent line of therapy where available) and between cycle 1 day 15-21. The biopsies will be performed under image guidance (including but not limited to CT or ultrasoundguided core biopsies) as determined by the location of tumor and risks associated with each procedure. Fresh tumor biopsies, on-site evaluations for tissue quality will be performed by the cytotechnologist to ensure viable tissue and for collection of adequate tumor sample. Four to 6 core biopsy samples will be collected. At a minimum, 2 will be placed in neutralbuffered formalin and embedded in paraffin wax and two core needle samples will be snap frozen and stored in liquid nitrogen. The tumor collected through these methods will be analyzed to explore whether positive vs negative biomarkers could predict response and resistance to the treatment. Samples will be retained after the clinical study report has been finalized.

#### 4.3.4.2 Molecular Analyses

These correlates will be analyzed using descriptive statistics to compare disease outcome in biomarker positive and negative subsets. In addition, univariate and multivariate analyses will be performed to see whether the markers described above (both as continuous or dichotomous variable) predict for disease outcome (i.e., disease control rate, response and PFS after appropriate adjustment for other prognostic variables).

# 4.3.4.3 Withdrawal of informed consent for donated biological samples

If a subject withdraws consent to the use of donated samples, the unused samples will be disposed of/destroyed, and the action documented.

The Principal Investigator:

• Ensures that biological samples from that subject, if stored at the study site, are immediately identified, disposed of /destroyed, and the action documented

• Ensures the laboratory(ies) holding the samples is/are informed about the withdrawn consent immediately and that samples are disposed/destroyed, the action documented and the signed document returned to the study site

• Ensures that the subject is informed about the sample disposal.

#### **Molecular studies**

The following molecular test results including but not limited to ALK, EGFR, K-ras, ROS-1, PD-L1 status, RET, Met, PTEN, BRAF, PI3K and Her2-neu will be conducted when appropriate or collected when available in the medical record. PD-L1 status by immunohistochemistry and quantitation of tumor infiltrating lymphocytes will be determined on all biopsy specimens.

#### Pharmacodynamic studies

NanoString Analysis. We will use a customized panel of ~100 genes (Custom Immune Panel) which will include genes in the NF-kB signature (30 genes with highest Principal Component Analysis (PCA) weight), resistance genes, T cell chemokines, T cell genes, HLA genes, co-stimulatory molecules and housekeeping genes (**Table 4**). Using this panel, we will separately evaluate expression by PCA of the NF-kB signature and a 12-gene T cell chemokine signature, which was also generated at Moffitt Cancer Center using bioinformatic gene expression analysis of 14,492 distinct solid tumors.

A key component of NanoString analysis will be to define resistance mechanisms in patients who fail to respond to treatment and those who progress after initially responding. A major mechanism of resistance may be the presence of other "driver" immunosuppressive mechanisms within the tumor microenvironment. These may include additional immune checkpoints (BTLA, LAG3, TIM3, A2AR), suppressive immune cells (Treg, TAMs), immunosuppressive enzymes (IDO, arginase), and/or immunosuppressive cytokines (TGFB, IL-10). NanoString studies will help determine whether pre-treatment and/or on-treatment expression of genes encoding for these additional immunosuppressive pathway components are associated with resistance to treatment. Depending on availability of biopsy samples, we will further determine protein expression of potentially important immunosuppressive molecules by IHC (see below). In patients who initially respond to therapy, there will be an option to also obtain a third biopsy upon progression of disease. Defining presence or emergence of resistance markers in these patients may therefore provide new insights into possible therapeutic strategies for this cohort of patients.

**RNA sequencing.** RNA sequencing (RNA-seq) can be used for exome wide analysis of gene expression. Depending on biopsy tissue availability, we will perform RNA-seq analysis to answer many of the same questions discussed above in NanoString studies. In addition, RNA-seq can help define new genes that may be associated with response and synergy between pembrolizumab and vorinostat as well as genes whose expression is changed as a result of treatment. If sufficient fresh frozen tissue is available, we will perform RNA-seq instead of NanoString studies.

*IHC studies.* Biopsy slides (FFPE) will be utilized to determine presence of CD8+ TILs and CD33+ myeloid cells. We will assess association of both cell types in pre-treatment biopsies

with patient response. In addition, we will determine changes in presence of these cell types as a result of treatment. We will also separately assess presence of these cell types in tumor beds and tumor stroma as they may differentially associate with response. Finally, if sufficient tissue is available, we will expand our studies to Vectra panels which rely on immunofluorescence to detect presence of multiple cell types. We will utilize panels which will include, but not limited to, FoxP3 (Treg marker), CK, CD3, CD4, CD8, Granzyme-B (to determine cytolytic activity of T cells), Ki67 (to determine T cell proliferation, which is associated with ongoing anti-tumor activity).

#### **5.0 METHODOLOGY**

# 5.1 Entry Criteria

# 5.1.1 Diagnosis/Condition for Entry into the Trial

1. Histologic or cytologic diagnosis of Stage IV NSCLC

# 5.1.2 Subject Inclusion Criteria

In order to be eligible for participation in this trial, the subject must:

- 1. Be willing and able to provide written informed consent/assent for the trial.
- 2. Be  $\geq$  18 years of age on day of signing informed consent.
- 3. Have measurable disease based on RECIST 1.1.
- 4. Have archival tissue where available. Those patients enrolled on the phase 1 escalation trial where archival tissue is not available will undergo a fresh biopsy where clinically feasible after discussion with the sponsor.

5. In addition, patients enrolled on the phase 1 dose escalation, phase 1 expansion or Phase II trial must be willing and able to provide tissue from a newly obtained core or excisional biopsy of a tumor lesion. Newly-obtained is defined as a specimen obtained up to 3 months prior to initiation of treatment on Day 1, and must be obtained after most recent treatment. Subjects for whom newly-obtained samples cannot be provided (e.g. inaccessible or subject safety concern) may submit an archived specimen only upon agreement from the Sponsor.)

- 6. Randomized phase II: Tumor proportional score of PD-L1 ≥1%.
- 7. Have a performance status of 0 or 1 on the ECOG Performance Scale.
- 8. Demonstrate adequate organ function as defined in **Table 5** all screening labs should be performed within 10 days of treatment initiation.
- 9. Have a histologic or cytologic diagnosis of Stage IV NSCLC.
- 10. Phase I/IB (Pre-treated): Have progression from at least one prior line of therapy. Maintenance therapy following platinum doublet-based chemotherapy is not considered as a separate regimen of therapy. Subjects who received platinum-containing adjuvant, neoadjuvant or definitive chemoradiation therapy given for locally advanced disease, and developed recurrent (local or metastatic) disease within 6 months of completing therapy are eligible for these arms. Subjects with recurrent disease ≥ 6 months after completing a platinum-containing adjuvant, neoadjuvant or definitive chemoradiation therapy given for locally advanced disease, who also subsequently progressed during or after a systemic regimen given to treat the recurrence, must have received another treatment in the first-line metastatic setting.
- 11. Randomized Phase II: Be treatment naïve in the stage IV setting, with the exception of patients whose tumors harbor an activating mutation (including but not limited to EGFR, ALK, ROS1) and were previously treated with targeted therapy. Subjects who received platinum-containing adjuvant, neoadjuvant or definitive chemoradiation therapy given for locally advanced disease, and developed recurrent (local or metastatic) disease < 6 months of completing therapy are ineligible for this arm. Subjects with recurrent disease ≥ 6 months after completing a platinum-containing adjuvant, neoadjuvant or definitive chemoradiation therapy given for locally advanced disease, who also subsequently progressed during or after a systemic regimen given to treat the recurrence, are eligible for this arm.

- 12. Female subjects of childbearing potential should have a negative urine or serum pregnancy within 72 hours prior to receiving the first dose of study medication. If the urine test is positive or cannot be confirmed as negative, a serum pregnancy test will be required.
- 13. Female subjects of childbearing potential should be willing to use 2 methods of birth control or be surgically sterile, or abstain from heterosexual activity for the course of the study through 120 days after the last dose of study medication (Reference Section 5.7.2). Subjects of childbearing potential are those who have not been surgically sterilized or have not been free from menses for > 1 year.

14. Male subjects should agree to use an adequate method of barrier contraception starting with the first dose of study therapy through 120 days after the last dose of study therapy.

**Table 5. Adequate Organ Function Laboratory/Test Values** 

System	Laboratory/Test Value
Hematological	
Absolute neutrophil count (ANC)	≥1,500 /mcL
Platelets	≥100,000 / mcL
Hemoglobin	≥9 g/dL
Renal	
Serum creatinine OR Measured or calculated a creatinine	≤1.5 X upper limit of normal (ULN) OR
clearance (GFR can also be used in place of creatinine or CrCl)	≥60 mL/min for subject with creatinine levels > 1.5 X institutional ULN
Hepatic	
Serum total bilirubin	≤ 1.5 X ULN OR
	Direct bilirubin ≤ ULN for subjects with total bilirubin levels > 1.5 ULN
AST (SGOT) and ALT (SGPT)	≤ 2.5 X ULN OR ≤ 5 X ULN for subjects with liver metastases
Albumin	≥2.5 mg/dL
Coagulation	
International Normalized Ratio (INR) or Prothrombin Time (PT)	≤1.5 X ULN unless subject is receiving anticoagulant therapy as long as PT or PTT is within therapeutic range of intended use of anticoagulants
Activated Partial Thromboplastin Time (aPTT)	≤1.5 X ULN unless subject is receiving anticoagulant therapy as long as PT or PTT is within therapeutic range of intended use of anticoagulants
Cardiac	
Left ventricular ejection fraction (LVEF)	
a Creatinine clearance should be calcula	ted per institutional standard.

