- 14. Has active autoimmune disease that has required systemic treatment in the past 2 years (i.e. with use of disease modifying agents, corticosteroids in doses greater than 10 mg of prednisone daily (or equivalent) or immunosuppressive drugs). Replacement therapy (eg., thyroxine, insulin, or physiologic corticosteroid replacement therapy for adrenal or pituitary insufficiency, etc.) is not considered a form of systemic treatment. Subjects are permitted to enroll if they have vitiligo, type I diabetes mellitus, residual hypothyroidism due to autoimmune condition only requiring hormone replacement, psoriasis not requiring systemic treatment, or conditions not expected to recur in the absence of an external trigger.
- 15. Has an active infection requiring systemic therapy.
- 16. Has a history or current evidence of any condition, therapy, or laboratory abnormality that might confound the results of the trial, that would substantially increase risk of incurring adverse events (AEs) from the study medications, that would interfere with the subject's participation for the full duration of the trial, or is not in the best interest of the subject to participate, in the opinion of the treating investigator.
- 17. Has known psychiatric or substance abuse disorders that would interfere with cooperation with the requirements of the trial.
- 18. Is pregnant or breastfeeding, or expecting to conceive or father children within the projected duration of the trial, starting with the pre-screening or screening visit through 120 days after the last dose of trial treatment.
- 19. Has a known history of Human Immunodeficiency Virus (HIV) (HIV 1/2 antibodies).
- 20. Has known active Hepatitis B (e.g., HBsAg reactive) or Hepatitis C (e.g., HCV RNA [qualitative] is detected).
- 21. Has received a live vaccine within 30 days of planned start of study therapy.

Note: Seasonal influenza vaccines for injection are generally inactivated flu vaccines and are allowed; however intranasal influenza vaccines (e.g., Flu-Mist®) are live attenuated vaccines, and are not allowed.

- 22. Has a history of, or any evidence of activenon-infectious pneumonitis that required or requires steroids.
- 23. Has evidence of interstitial lung disease
- 24. Has a history of symptomatic (NYHA class II-IV) heart failure.

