#### **AND**

- Experienced an investigator-determined confirmed radiographic disease progression after stopping their initial treatment with pembrolizumab
- Did not receive any anti-cancer treatment since the last dose of pembrolizumab
- Has a performance status of 0 or 1 on the ECOG Performance Scale
- Demonstrates adequate organ function as detailed in Section 5.1.2

- Female subject of childbearing potential should have a negative serum or urine pregnancy test within 72 hours prior to receiving retreatment with study medication.
- Female subject of childbearing potential should be willing to use 2 methods of birth control or be surgically sterile, or abstain from heterosexual activity for the course of the study through 120 days after the last dose of study medication (Reference Section 5.7.2). Subjects of child bearing potential are those who have not been surgically sterilized or have been free from menses for > 1 year.
- Male subject should agree to use an adequate method of contraception starting with the first dose of study therapy through 120 days after the last dose of study therapy.
- Does not have a history or current evidence of any condition, therapy, or laboratory abnormality that might interfere with the subject's participation for the full duration of the trial or is not in the best interest of the subject to participate, in the opinion of the treating investigator.

Subjects who restart treatment will be retreated at the same dose and dose interval as when they last received pembrolizumab. Treatment will be administered for up to one additional year.

Visit requirements are outlined in Section 6.0 – Trial Flow Chart.

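### The albumin row of Table 5 is written in mg/dL, which makes its limit too low to screen out any patient at entry or at re-treatment

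*Combined protocol and SAP*

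**What the plan says.** Section 5.1.2, inclusion criterion 8, requires that a subject "Demonstrate adequate organ function as defined in Table 5 all screening labs should be performed within 10 days of treatment initiation". The criterion is not limited to one phase, so it applies to all 108 planned patients (Section 1.0).

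Table 5 lists the limits by organ system. Under the hepatic heading, next to bilirubin and AST/ALT, stands "Albumin ≥2.5 mg/dL". In the same table the hemoglobin limit is 9 g/dL.

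Section 7.1.7.3, on the Second Course Phase, requires that a subject "Demonstrates adequate organ function as detailed in Section 5.1.2". The same albumin row is therefore in force again at re-treatment.

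Table 9 in Section 7.1.5 lists albumin among the chemistry tests, without a unit or reference range. No footnote or other section gives a different albumin limit or a different unit.

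**The concern.** A row in a table of adequate organ function is there to keep out patients whose value is too low. With the unit as printed, the limit lies so far below serum albumin values that the row cannot do this. It is not background text: criterion 8 makes it an operative entry condition, and Section 7.1.7.3 makes it a condition for re-treatment.

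Two things are at stake. The row as written gives no protection against entering a patient with very low albumin. And an eligibility checklist or database check copied from Table 5 would accept every value, so a monitor working from the written criterion could not record a low albumin as an eligibility deviation. Someone who mentally corrects the unit is applying a limit that the protocol does not state.

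**Working it through.** The plan derives no figure from this limit, so there is nothing of its own to reproduce. The check is a unit conversion, followed by an estimate of how many patients could be affected.

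**Inputs from the documents.** Albumin limit as written: 2.5 mg/dL (Table 5). Planned patients: 108, of whom 12 are in dose escalation (Section 1.0).

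**Inputs that are assumptions.** The documents give no albumin values. Two assumptions are used: a range of serum albumin from 0.5 g/dL (extremely low) to 5.0 g/dL (upper end of normal), and, for the size estimate, three normal distributions of albumin at screening.

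**Step 1, conversion.** 1 g/dL = 1,000 mg/dL, so 2.5 mg/dL ÷ 1,000 = 0.0025 g/dL.

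**Step 2, comparison with the written limit.** Ratio = (albumin in g/dL × 1,000) ÷ 2.5.

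| Assumed albumin (g/dL) | In mg/dL | Ratio to written limit | Passes as written | Would pass if the unit were g/dL |
|---|---|---|---|---|
| 0.5 | 500 | 200 | yes | no |
| 1.0 | 1,000 | 400 | yes | no |
| 1.5 | 1,500 | 600 | yes | no |
| 2.0 | 2,000 | 800 | yes | no |
| 2.5 | 2,500 | 1,000 | yes | yes |
| 3.5 | 3,500 | 1,400 | yes | yes |
| 5.0 | 5,000 | 2,000 | yes | yes |

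Every assumed value passes as written. The last column is for illustration only, since the documents do not say what unit was meant.

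**Step 3, how many patients a g/dL limit would concern.** With albumin at screening taken as normal with mean μ and standard deviation σ, the share below 2.5 g/dL is Φ((2.5 − μ)/σ).

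| μ, σ (g/dL, assumed) | (2.5 − μ)/σ | Share below 2.5 | Expected of 108 | Expected of 12 |
|---|---|---|---|---|
| 3.8, 0.45 | −2.89 | 0.2% | 0.2 | 0.02 |
| 3.7, 0.5 | −2.40 | 0.8% | 0.9 | 0.1 |
| 3.5, 0.6 | −1.67 | 4.8% | 5.2 | 0.6 |

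The range is about 0 to 5 patients in the whole trial, and less than one in dose escalation.

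**Step 4, what else in the documents could stop such a patient.**

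- Exclusion criterion 16 (Section 5.1.3) covers a patient who "Has a history or current evidence of any condition, therapy, or laboratory abnormality that might confound the results of the trial", and also an abnormality that would substantially raise the risk of adverse events. It depends on the treating investigator's opinion and gives no number.
- The text under Table 9 requires laboratory results to be reviewed and judged acceptable before each dose. Again there is no number.
- Section 7.1.7.3 has its own condition on laboratory abnormalities at re-treatment, also a matter of the investigator's opinion.
- Table 5 keeps its numeric limits for bilirubin, AST/ALT and INR/PT. These bear on liver function but say nothing about albumin.

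None of these puts a numeric albumin limit back.

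**The case against.** The strongest reply is that this is a transparent slip. Many readers will see g/dL, the safeguards in step 4 stand between a patient with very low albumin and the first dose, and the number of patients concerned is small even on the least favorable assumption. Much of this stands. The safeguards are real, so the statement that nobody is excluded is true of this row only, not of enrollment as a whole. The patient numbers also rest on assumed distributions that the documents do not supply. What does not stand is that the slip is therefore harmless as text: a criterion that works only when the reader replaces its unit is not an objective criterion.

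A reader might infer four stronger things, and the documents support none of them.

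- That the limit is a thousand times below any patient's value. The factor is 1,000 only against 2.5 g/dL. Over the assumed range it runs from 200 to 2,000.
- That the two recruiting centers (Section 10.2) will apply different entry rules. That is possible, but nothing in the documents shows it.
- That the dose-limiting toxicity assessment is compromised. The expected number in the 12-patient dose escalation is 0.02 to 0.6, and no DLT definition refers to albumin.
- That the intended limit is known to be 2.5 g/dL. The hemoglobin row suggests the unit, but hemoglobin is a different analyte, and only the sponsor can say what was meant.

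**Conclusion.** Wrong as written, and of low severity. It is a unit error in an operative eligibility threshold, not a fault in any calculation of the plan. That the row excludes nobody rests on the unit conversion and on the assumption that serum albumin is at least 0.5 g/dL, which could be far too high without changing the result: the written limit is 200 times lower still. The size, about 0 to 5 of 108 patients, rests on two further assumptions: that the unit was meant to be g/dL with the number unchanged, and that albumin at screening follows one of the three distributions shown. No sample size, power, type I error or endpoint definition depends on this row.

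**What to change.** The sponsor should confirm the intended albumin limit and its unit, noting that hemoglobin in Table 5 is given in g/dL, and correct the albumin row accordingly. Any eligibility checklist or database check built on Table 5 should be corrected at the same time. Section 7.1.7.3 needs no edit of its own, because it refers back to Section 5.1.2.

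The cost is one table entry in the next amendment plus the checklist. No extra test is needed: albumin is already in the Table 9 chemistry tests, and the serum chemistry panel is scheduled at screening in the Section 6.1 flow chart.
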